Hypothesis: UPA will decrease bleeding and spotting days in users of the ENG implant with unscheduled bleeding by 30% when compared to placebo as assessed by daily bleeding diaries.

SECONDARY AIMS (SA)

SA1: To evaluate bleeding cessation rates by day 10 following seven days of treatment with either ulipristal acetate or placebo.

SA2: To evaluate participant satisfaction with regards to bleeding pattern after use of ulipristal acetate.

SA3: To evaluate participant satisfaction with regards to medication side effects.

SA4: To evaluate effect, if any, of ulipristal acetate on ovulatory status.

KEY STUDY MEASURES

PRIMARY AIM

1. Daily SMS text message bleeding diaries (Day 1 – Day 30)

SECONDARY AIMS

1. SMS text message bleeding diaries Day 1 – Day 10
2. Phone/in-person survey to assess satisfaction with bleeding pattern at 1, 2, 3, and 4 weeks post-study enrollment
3. Phone/in-person survey to assess satisfaction with medication side effects at 1, 2, 3, and 4 weeks post-study enrollment
4. Serum progesterone levels at baseline and at 1, 2, 3, and 4 weeks post-study enrollment

STUDY DESIGN

The INTERRUPT study is a single-site, double-blinded, randomized, placebo-controlled clinical trial. The total sample size for this study is 104. Of these participants, a subset will undergo weekly venipuncture to assess serum progesterone levels.

RANDOMIZATION SCHEME

A block randomization scheme will be created using a computerized random number generator. In order to keep the research team and participants blinded, assignment will be done by the pharmacy based on this randomization scheme. The pharmacy will make identical UPA and placebo capsules, dispensed as a labeled outpatient prescription after a participant is randomized. The randomization scheme will be generated by a random number table with an allocation ratio of 1:1 in blocks of four with a total of 52 participants in each group for a total sample size of 104.

DESCRIPTION OF METHODS

ULIPRISTAL ACETATE

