Fifty-two participants will be enrolled per arm, for a total of 104 patients. Previous studies evaluating interventions for implant bleeding have defined a clinically significant difference as a decrease in bleeding/spotting days by 20-40%.^{22,23} Therefore, our effect size will be a 30% decrease in the amount of bleeding/spotting days. The sample size calculation used for this study assumes a standard deviation of 10, an alpha of 0.05, power of 80%, and accounting for 15% drop-out. This standard deviation is based on a previous study that found the standard deviation for the mean number of bleeding/spotting days to be approximately +/- 10 days.²²

STATISTICAL METHODS

Demographics will be presented with descriptive statistics stratified by randomization group. Student t tests, chi-square, and Fisher Exact tests will be used, where appropriate, to compare characteristics of participants receiving ulipristal acetate to those receiving placebo. For the primary outcome, mean number of bleeding days in the 30 days following intervention, if normally distributed, we will use a t-test. If not normally distributed, the Mann-Whitney U test will be employed. These tests will also be employed for our secondary outcomes of bleeding pattern satisfaction, medication side-effect satisfaction, and contraceptive efficacy. For the secondary outcome regarding cessation of bleeding by day 10, as this outcome is dichotomous, we will use a Chi-square test (or Fisher Exact test, if appropriate).

MISSING DATA

Missing data rates and patterns will be assessed twice weekly by the data manager and remedial measures, including re-abstraction of data and retraining of staff, will be used as needed to minimize missing data.

ETHICAL CONSIDERATIONS

INSTITUTIONAL REVIEW BOARD

Washington University School of Medicine in St. Louis, MO, has applied for and been approved through the Washington University School of Medicine's Institutional Review Board (IRB) office (protocol number #201612002).

INFORMED CONSENT

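### Satisfaction is rated in four weeks for each of two secondary aims, but the plan names only a two-sample test and does not say which week, summary or model answers either aim

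*Combined protocol and SAP*

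**What the plan says.** Key Study Measures, under Secondary Aims, lists the two outcomes separately: "Phone/in-person survey to assess satisfaction with bleeding pattern at 1, 2, 3, and 4 weeks post-study enrollment" and "Phone/in-person survey to assess satisfaction with medication side effects at 1, 2, 3, and 4 weeks post-study enrollment". Each woman can therefore contribute four ratings to each aim.

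Statistical Methods proposes a t-test for the primary outcome, with a fallback: "If not normally distributed, the Mann-Whitney U test will be employed". It then extends the pair to the satisfaction outcomes: "These tests will also be employed for our secondary outcomes of bleeding pattern satisfaction, medication side-effect satisfaction, and contraceptive efficacy". It gives no week, no summary over the four weeks, no model for repeated ratings and no multiplicity rule. The Missing Data section covers prevention and data checking only. It does not say how a missed weekly survey is handled in the analysis.

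The other main outcomes do not share this gap. The primary outcome is one count per woman over 30 days, and SA1 is fixed at day 10.

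**The concern.** A two-sample test needs one number per woman, and the plan collects four without saying which one enters the test. An analyst following the text has to choose a week, form a summary, or test every week. If that choice is made after the data are seen, the most favourable week could be reported as the satisfaction result.

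The weeks are not interchangeable. Description of Methods has study drug taken from Day 0 to Day 6, so week 1 covers treatment and weeks 2 to 4 follow it. Under Follow-Up and Retention, the standard subset answers about the past week and the progesterone subset about the time since the last appointment, so a week 4 rating does not stand for the month. In the standard subset, gift cards after enrollment are tied to the week 2 and week 4 surveys, so completion could differ by week. A single-week test drops any woman who missed that week, even if she answered the other three surveys.

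**Working it through.** **The plan's own figure.** The only computed figure is the sample size for the primary outcome. Its inputs under Sample Size are "The sample size calculation used for this study assumes a standard deviation of 10", "our effect size will be a 30% decrease in the amount of bleeding/spotting days" and "an alpha of 0.05, power of 80%, and accounting for 15% drop-out". The control mean is not stated. Assuming 20 days (a difference of 6) and a two-sided test, n = 2 × (1.960 + 0.842)² × 10² / 6² = 43.6, so 44 per arm, and 44 / 0.85 = 51.8, so 52. This matches the plan, but only at an assumed mean near 20: a mean of 18 gives 64 per arm and 22 gives 44. No calculation is given for satisfaction. Only the evaluable number is needed below: 52 × 0.85 = 44 per arm.

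**Number of possible tests.** 2 aims × 4 weeks = 8 at most.

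**Chance of at least one false positive, if every week is tested at 0.05 and any one counts.**
- Independent tests: 1 − 0.95⁴ = 18.5% per aim; 1 − 0.95⁸ = 33.7% over both.
- Correlated tests, by simulation: the documents give no within-woman correlation ρ, so it is assumed. Per aim the chance is 17% at ρ = 0.3, 16% at 0.5, 13% at 0.7 and 9% at 0.9.
- Over eight tests with unrelated aims, it is 29% at ρ = 0.5 and 24% at 0.7. A between-aim correlation of 0.3 gives 27% and 24%.

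**Precision of a four-week average.** With equal correlation between weeks and complete data, its variance relative to a single week is (1 + 3ρ)/4.
- ρ = 0.5: (1 + 1.5)/4 = 0.625, a 38% reduction; SE ratio 0.79.
- ρ = 0.7: (1 + 2.1)/4 = 0.775, a 23% reduction; SE ratio 0.88.

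With 44 per arm, the difference detectable with 80% power in a single week is (1.960 + 0.842) × √(2/44) = 0.60 SD. For the average it is 0.47 SD at ρ = 0.5 and 0.53 SD at ρ = 0.7. For a constant 0.5 SD effect, power rises from 65% to 84% or 76%.

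**When the average does worse.** Suppose an effect of 0.6 SD in week 1 and none afterwards. A week 1 test has 80% power. The average effect is 0.6/4 = 0.15 SD, with power of 17%, 14% or 12% at ρ = 0.3, 0.5 or 0.7. If the effect fades through 0.6, 0.4, 0.2 and 0 SD, the average is 0.3 SD, and power is 43% at ρ = 0.5 and 36% at ρ = 0.7.

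**Gain for one named week.** For a week 4 contrast with complete data, a repeated-measures model gives the same SE as the two-sample test (ratio 1.00). With 15% monotone dropout, the ratio is 0.98 at ρ = 0.5 and 0.96 at ρ = 0.7.

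**The case against.** A reader might infer that the plan commits to eight separate weekly tests. It does not. Statistical Methods is silent on the number of tests, and one test at week 4 or on each woman's four-week mean would fit the sentence equally well. The false-positive figures therefore describe one permitted reading, and the independent-test values are a ceiling, since ratings from the same woman will be correlated. This part of the objection stands.

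A reader might also infer that a repeated-measures model is simply more precise. The gain comes from averaging over weeks. With complete data, the plan's own t-test on each woman's four-week mean would match it. For a single week, the model gains nothing with complete data and little with 15% dropout. The documents give no expected rate of missed surveys, and they describe repeat calls, email and an alternate contact to recover them. This stands too. The model's remaining advantage is that it uses all available surveys when some are missed.

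The third tempting step is to make the four-week average the test for both aims. That does not suit SA3. Later surveys ask mostly about time off drug, and Investigator Monitoring ties side-effect collection to the period of study medication, so an average could dilute an early effect severely.

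Finally, the satisfaction scale is not described, so a specific model form cannot be prescribed. None of these points tells the analyst which of the four ratings answers the aim.

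**Conclusion.** The point holds as an unspecified time point or summary for SA2 and SA3, with a better method available at little cost. Following the text as it stands either leaves three of four ratings unused or gives up to four p-values per aim with no rule for choosing among them. The 13% to 19% chance of a false positive per aim applies only if all four weeks are tested and any one counts; 13% rests on an assumed correlation of 0.7, and 19% on independence. The 23% to 38% variance reduction belongs to the four-week average, at assumed correlations of 0.7 to 0.5.

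The documents do not support saying that eight tests are planned, that a model beats the named tests whatever the contrast, or that the four-week average is right for side effects. These are secondary aims, so this is an inexpensive improvement and not a threat to the trial's main conclusion.

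**What to change.** Before unblinding, amend Statistical Methods as follows.
- For each of SA2 and SA3, fit one repeated-measures model suited to the satisfaction scale (linear or ordinal mixed model, for example), with arm, week, arm-by-week and woman as a random effect, using all available surveys.
- For SA2, name the arm effect averaged over weeks 1 to 4 as the single test. It corresponds to the 30-day period of the primary outcome.
- For SA3, do not default to that average. Name one contrast in advance, chosen in light of the Day 0 to Day 6 dosing window.
- Show the other weekly estimates descriptively.

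This leaves two pre-named tests in place of up to eight. The same sentence of the plan also covers contraceptive efficacy, measured by "Serum progesterone levels at baseline and at 1, 2, 3, and 4 weeks post-study enrollment" in the 40-woman subset, so a similar rule could be stated there.

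The cost is SAP wording and slightly more analysis, with no new data, visits or participants. The downside is that the SA2 average loses power relative to an early week if the effect fades. The weekly estimates would show such a pattern but would not restore the power.
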